7.1.2. Serious Adverse Events

A serious adverse event (SAE) is defined as an event that, at any dose, results in the following:

- Death
- Life-threatening (Note: The term "life-threatening" in the definition of "serious" refers to an event in which the subject was at risk of death at the time of the event; it does not refer to an event that hypothetically might have caused death if it were more severe.)
- In-patient hospitalization or prolongation of existing hospitalization

- Persistent or significant disability/incapacity
- A congenital anomaly/birth defect
- A medically important event or reaction: such events may not be immediately life-threatening or result in death or hospitalization but may jeopardize the subject or may require intervention to prevent one of the other outcomes constituting SAEs. Medical and scientific judgment must be exercised to determine whether such an event is reportable under expedited reporting rules. Examples of medically important events include intensive treatment in an emergency room or at home for allergic bronchospasm; blood dyscrasias or convulsions that do not result in hospitalization; and development of drug dependency or drug abuse. For the avoidance of doubt, infections resulting from contaminated medicinal product will be considered a medically important event and subject to expedited reporting requirements.

7.1.3. Clinical Laboratory Abnormalities and Other Abnormal Assessments as Adverse Events or Serious Adverse Events

Laboratory abnormalities without clinical significance are not recorded as AEs or SAEs. However, laboratory abnormalities (eg, clinical chemistry, hematology, and urinalysis) that require medical or surgical intervention or lead to IMP interruption, modification, or discontinuation must be recorded as an AE, as well as an SAE, if applicable. In addition, laboratory or other abnormal assessments (eg, electrocardiogram, x-rays, vital signs) that are associated with signs and/or symptoms must be recorded as an AE or SAE if they meet the definition of an AE or SAE as described in Sections 7.1.1 and 7.1.2. If the laboratory abnormality is part of a syndrome, record the syndrome or diagnosis (eg, anemia), not the laboratory result (ie, decreased hemoglobin).

7.2. Assessment of Adverse Events and Serious Adverse Events

The investigator or qualified subinvestigator is responsible for assessing AEs and SAEs for causality and severity, and for final review and confirmation of accuracy of event information and assessments.

7.2.1. Assessment of Causality for Study Drugs and Procedures

The investigator or qualified subinvestigator is responsible for assessing the relationship to IMP therapy using clinical judgment and the following considerations:

- No: Evidence exists that the adverse event has an etiology other than the IMP. For SAEs, an alternative causality must be provided (eg, pre-existing condition, underlying disease, intercurrent illness, or concomitant medication).
- Yes: There is reasonable possibility that the event may have been caused by the investigational medicinal product.

It should be emphasized that ineffective treatment should not be considered as causally related in the context of adverse event reporting.

The relationship to study procedures (eg, invasive procedures such as venipuncture or biopsy) should be assessed using the following considerations:

- No: Evidence exists that the adverse event has an etiology other than the study procedure.
- Yes: The adverse event occurred as a result of protocol procedures, (eg, venipuncture)

7.2.2. Assessment of Severity

The severity grading of AEs will be assessed as Grade 1, 2, 3, or 4 according to the Common Terminology Criteria for Adverse Events (CTCAE) Version 4.03, which can be found at http://evs.nci.nih.gov/ftp1/CTCAE/CTCAE_4.03_2010-06-14_QuickReference_5x7.pdf.

For AEs associated with laboratory abnormalities, the event should be graded on the basis of the clinical severity in the context of the underlying conditions; this may or may not be in agreement with the grading of the laboratory abnormality.

The distinction between the seriousness and the severity of an adverse event should be noted. Severe is a measure of intensity; thus, a severe reaction is not necessarily a serious reaction. For example, a headache may be severe in intensity, but would not be classified as serious unless it met one of the criteria for serious events listed above.

7.3. Investigator Requirements and Instructions for Reporting Adverse Events and Serious Adverse Events to Gilead

Requirements for collection prior to study drug initiation:

After informed consent, but prior to initiation of study medication, the following types of events should be reported on the case report form (eCRF): all SAEs and adverse events related to protocol-mandated procedures.

Adverse Events

Following initiation of study medication, collect all AEs, regardless of cause or relationship, until 30 days after last administration of study IMP must be reported to the eCRF database as instructed. During the post-treatment follow-up period (through Week 24), AEs including SAEs related to protocol mandated procedures must be collected and reported to the eCRF database.

All AEs should be followed up until resolution or until the adverse event is stable, if possible. Gilead Sciences may request that certain AEs be followed beyond the protocol defined follow up period.

Serious Adverse Events

All SAEs including deaths, regardless of cause or relationship, that occurs after the subject first consents to participate in the study (ie, signing the informed consent) until 30days after the last dose of study IMP must be reported to the eCRF database and Gilead Drug Safety and Public Health (DSPH) as instructed. This also includes any SAEs resulting from protocol-associated procedures performed after informed consent is signed. During the post-treatment follow-up period (through Week 24) any SAEs deemed related to the use of study IMP should also be reported.

Investigators are not obligated to actively seek SAEs after the protocol defined follow up period. However, if the investigator learns of any SAEs that occured after study participation has concluded and the event is deemed relevant to the use of IMP, he/she should promptly document and report the event to Gilead DSPH.

- All AEs and SAEs will be recorded in the eCRF database within the timelines outlined in the eCRF completion guideline.
- Electronic Serious Adverse Event (eSAE) Reporting Process
- Site personnel record all SAE data in the eCRF database and from there transmit the SAE information to Gilead DSPH within 24 hours of the investigator's knowledge of the event. Detailed instructions can be found in the eCRF completion guidelines.
- If for any reason it is not possible to record the SAE information electronically, ie, the eCRF database is not functioning, record the SAE on the paper serious adverse event reporting form and submit within 24 hours to:

Gilead Sciences DSPH	[contact]
	E-mail:	[contact]

- As soon as it is possible to do so, any SAE reported via paper must be transcribed into the eCRF Database according to instructions in the eCRF completion guidelines.
- If an SAE has been reported via a paper form because the eCRF database has been locked, no further action is necessary.
- For fatal or life-threatening events, copies of hospital case reports, autopsy reports, and other documents are also to be submitted by e-mail or fax when requested and applicable. Transmission of such documents should occur without personal subject identification, maintaining the traceability of a document to the subject identifiers.

- Additional information may be requested to ensure the timely completion of accurate safety reports.
- Any medications necessary for treatment of the SAE must be recorded onto the concomitant medication section of the subject's eCRF and the event description section of the SAE form.

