Study Procedures/ Frequency:	Screening assessments should be completed within 14 days of Baseline/Day 1 visit. Eligibility will be based on local laboratory testing. Refer to Section 6.9.10 Screening Laboratory Assessments for additional details.
	After the Screening period and a randomization visit at Baseline/Day 1, study visits will occur on Weeks 1, 2, 3, 4, 6, 8, 12, 16, 20, and 24. At minimum, vital signs, physical examination (PE), HE and ascites assessment, safety laboratory tests, alcohol consumption, and concomitant medications will be done at every visit. AEs will be collected up to 30 days after the last dose of any study drug and SAEs will be collected throughout the study.
	During the hospitalization period, subjects will be evaluated daily with assessments to include a review of adverse events, concomitant medications, study drug adherence, and a symptom-directed PE including assessments for ascites and HE. Findings based on these assessments and laboratory investigations obtained by treating physicians as part of routine care will be assessed by the investigator for triggers that may necessitate further evaluation and/or treatment discontinuation and managed per Section 7 of the protocol.

PPD

Screening assessments will include complete medical history, PE including vital signs, HE, ascites, hepatorenal syndrome (HRS) and infection assessment, laboratory assessments (hematology, chemistry, coagulation tests, HIV serology, hepatitis B and C serologies, and urinalysis), pregnancy tests (for females of child-bearing potential), liver biopsy, liver ultrasound, standard 12-lead ECG, chest x-ray, AUDIT / SADQ questionnaires, adverse events and concomitant medication assessment.

Recent gastrointestinal bleeding:

Gastrointestinal bleeding will be treated and the subject stabilized during the Screening period for at least 48 hours prior to randomization.

Sepsis:

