6.5.2. Weeks 8, 16, and 20 / Post Treatment Visits (± 5 Days)

During the Week 8, 16, and 20 post treatment visits, the following will be performed and documented:

- Assess alcohol consumption
- Complete PE including, vital signs
- Perform standard 12-lead ECG (Week 8 only)
- Assessments for HE, ascites, HRS and infection
- Obtain blood samples for:
 - Hematology
 - Chemistry: ALT, AST, albumin, alkaline phosphatase, bicarbonate, BUN, calcium, chloride, creatinine, glucose, LDH, magnesium, phosphorus, potassium, sodium, total and direct bilirubin, total protein, uric acid, GGT
 - Coagulation Tests: PT, PTT, and INR
 - Blood for Biomarkers (Week 8 only)
- Urine pregnancy test (for females of childbearing potential)
- Record all concomitant medications that the subject has taken since the previous visit
- Record any serious adverse events and all adverse events occurring since the previous visit (Week 8 only)
- Record procedure-related adverse events and procedure-related SAEs as well as any SAEs that the investigator deems relevant to the use of study drug for Weeks 16 and 20 only
- Subjects that have their scheduled Week 8 visit prior to Day 56 will require a phone contact between Day 56-63 respectively, to assess for mortality and liver transplantation.

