6.5.3. Weeks 12 and 24 / Post Treatment Visits (± 5 Days)

Subjects that have their scheduled Week 12 or Week 24 visit prior to Day 84 or Day 168, will require a phone contact between Day 84-91 or Day 168-175 respectively, to assess for mortality and liver transplantation.

During the Week 12 and Week 24 post treatment visits, the following will be performed and documented:

- QoL Questionnaire (CLDQ, week 24 only)
- Assess alcohol consumption
- Assessments for HE, ascites, HRS and infection
- Complete PE including, vital signs, and body weight
- Obtain blood samples for:
 - Hematology
 - Chemistry: ALT, AST, albumin, alkaline phosphatase, bicarbonate, BUN, calcium, chloride, creatinine, glucose, LDH, magnesium, phosphorus, potassium, sodium, total and direct bilirubin, total protein, uric acid, GGT
 - Coagulation Tests: PT, PTT, and INR
 - Blood for Biomarkers; Urine for Biomarkers (Week 24 only)
 - ELF^{TM} Test and LOXL2
 - Insulin
 - Hemoglobin A1c
 - Lipid Profile
- Stool for microbiome testing (week 24 only)
- Urine pregnancy test (for females of childbearing potential)
- Record all concomitant medications that the subject has taken since the previous visit
- Record all serious adverse events and any study related adverse events occurring since the previous visit

- Record procedure-related adverse events and procedure-related SAEs as well as any SAEs that the investigator deems relevant to the use of study drug (Week 24 only)
- FibroScan (if available and for subjects without ascites [Week 24 only])

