6.6. Unscheduled Visits

Additional unscheduled assessments may be performed at the discretion of the investigator. At a minimum, the following will be performed and documented, unless the unscheduled visit is only to refill medication, then the following procedures are not necessary.

- Record all concomitant medications that the subject has taken since the previous visit
- Record any serious adverse events and all adverse events occurring since the previous visit
- Assessments for HE, ascites, HRS and infection
- Obtain blood samples for:
 - Hematology
 - Chemistry: ALT, AST, albumin, alkaline phosphatase, bicarbonate, BUN, calcium, chloride, creatinine, glucose, LDH, magnesium, phosphorus, potassium, sodium, total and direct bilirubin, total protein, uric acid, GGT
 - Coagulation Tests: PT, PTT, and INR

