6.9.9. Infection

The occurrence of bacterial, fungal, or viral infections should be recorded as adverse events. Relevant data to be recorded include the source of infection, date of onset/resolution, presence of fever (temperature $\geq 38^{\circ}$ C/100.4°F), laboratory investigations (e.g. white blood cell count, cultures, chest x-ray), and anti-microbial therapy. An infection will be considered definite in subjects with clinical evidence of infection and a positive culture from a normally sterile source (with the exception of spontaneous bacterial peritonitis [SBP] as below). All other infections will be considered probable. In subjects with ascitic fluid neutrophils ≥ 250 cells/mm³, definite SBP will be recorded irrespective of culture positivity.

If pneumonia develops during the study, treatment according to the following guidelines is recommended:

- Community-Acquired Pneumonia: Infectious Diseases Society of America/American Thoracic Society Consensus Guidelines (2007) (http://cid.oxfordjournals.org/content/44/Supplement 2/S27.full)
 - The minimum recommended duration of antibiotic treatment is 5 days.
- Hospital-Acquired Pneumonia (HAP): Infectious Diseases Society of America/American Thoracic Society Consensus Guidelines (2016) (http://www.idsociety.org/Guidelines/Patient_Care/IDSA_Practice_Guidelines/Infections_by Organ System/Lower/Upper Respiratory/Hospital-Acquired Pneumonia (HAP)/)
 - HAP is defined as a pneumonia not incubating at the time of hospital admission and occurring \geq 48 hours after admission.
 - The minimum recommended duration of antibiotic treatment is 7 days.

SBP, UTI, and other infections that develop during the study should be treated according to the following guidelines:

- SBP: AASLD Practice Guidelines: Management of Adult Patients with Ascites Due to Cirrhosis: Update 2012. (http://www.aasld.org/publications/practice-guidelines-0#practice_guidelines_accordion-block-2). The minimum recommended duration of antibiotic treatment is 5 days. Patients with SBP who also have a serum creatinine
 1 mg/dL, blood urea nitrogen > 30 mg/dL, or total bilirubin > 4 mg/dL should also receive 1.5 g albumin per kg body weight within 6 hours of detection and 1.0 g/kg 2 days later.

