Liver Ultrasound		x	2		8				8		3										
Review Concomitant Medications		x	ŝ	X		X		X		X		X	x	x	X	X	X	x	X	X	

GS-4997 Protocol GS-US-416-2124 Gilead Sciences, Inc.

	Screening ^a			Treatment ^b					Post	Treatme	nt			Unscheduled Visit	
		Baseline/	Week 1	Week 2	Week 3	Week 4/ EoT ^t	Week 6	Week 8 ^u	Week 12 ^u	Week 16	Week 20	Week 24 ^u	Follow Up visit ^v		
	-14 days	Day 1			±3 days						±5 days				
Adverse Events	X	Х	Х	X	Х	X	X	Х	X	Х	X	X	X	x	
Sparse PK Sample ^p		Х	Х	X		X ^p									
Stool Collection		Х				X						X			
Randomization ^q		X			2			-				-			
GS-4997 Dispensing		Х													
Prednisolone Dispensing		X	X	E E	X						3				
PPD															
Genomic Sample ^s		Х				-		-					-		
Study Drug Adherence			Х	X	х	X									
FibroScan ^w		X				X						X			
Lille Score ^x			Х	X	Х	X									

a The visit window may be extended under special circumstances with explicit approval of the Medical Monitor. Subjects who fail to meet eligibility criteria due to an abnormal laboratory result may undergo re-testing of the abnormal analyte once during the Screening window. This will be done at the discretion of the investigator and also with prior approval of the Medical Monitor. The following laboratory tests will be collected at Screening for testing at both the local and central laboratories: urine drug screen, hematology, chemistry, and coagulation tests. Eligibility will be based on local laboratory results. For urine drug screen, local laboratory testing done within 10 days of the Screening visit may be used to determine eligibility. For hepatitis B serology, hepatitis C serology, and HIV serology, these tests will be sent to both the local and central laboratory and be the basis for eligibility. A serum pregnancy test will be sent only to the central laboratory at Screening.

b During the hospitalization period, subjects will be evaluated daily with assessments to include a review of adverse events, concomitant medications, study drug adherence, and a symptom-directed PE including assessments for ascites and HE. Findings based on these assessments and laboratory investigations obtained by treating physicians as part of routine care will be assessed by the investigator for triggers that may necessitate further evaluation and/or treatment discontinuation and managed accordingly per Section 7 of the protocol.

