c A Legally Authorized Representative may assist the subject in completing the questionnaires. If the subject is unable or refuses to complete a questionnaire, this should be documented on the relevant eCRF.

- d Perform a complete Physical Exam with a focus on ascites and encephalopathy.
- e Please see Section 6.9 for description of assessments and record diagnosis/abnormal findings as an AE.

f Drug screen for amphetamines, cocaine and opiates (ie heroin, morphine).

- g Urinalysis (routine and microscopic) and culture to be performed by local lab.
- h Subjects with evidence of sepsis or gastrointestinal bleeding may be treated for a minimum of 2 days with appropriate antibiotics. Once deemed stable, subject may continue Screening and randomized if eligible.
- i Chemistry will include: alanine aminotransferase (ALT), aspartate aminotransferase (AST), albumin, alkaline phosphatase, bicarbonate, blood urea nitrogen, calcium, chloride, creatinine, glucose, lactate dehydrogenase (LDH), magnesium, phosphorus, potassium, sodium, total and direct bilirubin, total protein, uric acid, gamma-glutamyl transferase (GGT). Chemistry must be collected for both local and central lab at Baseline/Day1, Week 1, Week 2, Week 3, and Week 4 for Lille Score
- j Local laboratory results for Hepatitis B and C and HIV Serology done within 10 days of the Screening visit may be used to determine eligibility.
- k Coagulation Panel includes: PT, PTT and INR. Coagulation must be collected for both local and central lab at Baseline/Day visit for Lille Score.
- 1 Females of childbearing potential only. Serum pregnancy test at Screening done at central lab. Urine pregnancy test at Screening and other visits.
- m Paracentesis with ascitic fluid cell count, differential, and culture will be performed if clinically-detectable ascites is present.
- n Liver biopsy obtained during the current hospital admission prior to Screening is acceptable. Liver biopsy can be performed up to 7 days post Baseline/Day 1. However, if biopsy results are not consistent with AH, the subject will discontinue study drug within 3 days of receipt of liver biopsy result, attend an EoT visit as soon as possible and attend a 30-day FU visits and be withdrawn from the study. If the liver biopsy sample is inadequate for a pathologic diagnosis of AH, but does not reveal an alternative etiology, the subject may remain in the study.

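### After last dose plus 30 days the protocol's rules on recording infections and HRS conflict, while the SAP counts both from the AE eCRF to end of study, so late unrelated events may be missed

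*Protocol*

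**What the plan says.** The recording rules for the time after last dose plus 30 days fall into three groups.

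- **Narrow.** Protocol 7.3 collects all AEs and SAEs, whatever their cause, until 30 days after the last dose. For later follow-up it says "During the post-treatment follow-up period (through Week 24), AEs including SAEs related to protocol mandated procedures must be collected", and its SAE paragraph adds SAEs judged related to study drug. Section 6.5.2 gives the same rule for Weeks 16 and 20: "Record procedure-related adverse events and procedure-related SAEs as well as any SAEs that the investigator deems relevant to the use of study drug".
- **Broader for SAEs.** The synopsis (Study Procedures) says "AEs will be collected up to 30 days after the last dose of any study drug and SAEs will be collected throughout the study". Section 6.5.3, for Weeks 12 and 24, says "Record all serious adverse events and any study related adverse events occurring since the previous visit" and then repeats the narrow rule for Week 24.
- **Broad.** Section 6.9.9 says "The occurrence of bacterial, fungal, or viral infections should be recorded as adverse events", with no limit of time or cause. In Appendix 2 the HRS and infection rows run to Week 24 and carry footnote e: "Please see Section 6.9 for description of assessments and record diagnosis/abnormal findings as an AE". The "Adverse Events" row is also marked at every visit to Week 24. Section 6.6 asks at unscheduled visits: "Record any serious adverse events and all adverse events occurring since the previous visit". SAP 1.2 describes AEs and SAEs tied to study endpoints, naming infections and HRS, as collected for the whole study; only other SAEs stop at last dose plus 30 days.

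SAP 6.2.7 finds infections from AEs flagged as infection on the AE eCRF, and HRS from the AE preferred term after medical monitor review. Tables 15.9.2.3.1 to 15.9.2.3.4 and 15.9.2.4.1 to 15.9.2.4.2 count both to end of study.

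**The concern.** Whether a late infection or HRS event reaches the AE eCRF depends on which passage the site followed. The events exposed are the ones of interest. Protocol 7.2.1 gives underlying disease as an example of an alternative cause and says that ineffective treatment is not a causal relation, so HRS or infection in a failing liver can properly be judged unrelated. Deaths and transplants are safe because they have their own forms (SAP 6.2.1, 6.2.2). No second source feeds the infection and HRS counts. At stake are two secondary endpoints whose percentages may read low for the later part of follow-up.

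Two smaller conflicts over follow-up touch the same tables: subjects in the mITT set who leave the study by design, and Appendix 2 footnote t. Both are checked below.

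**Working it through.** The plan gives no figure to reproduce, so the check is a reading of the text plus day counts.

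**Reading of 7.3.** The quoted sentence could be parsed as requiring all AEs. Its context is against that: the sentence before it ends all-cause collection at 30 days, the SAE paragraph then adds drug-related SAEs, and 6.5.2 spells out the narrow rule. The narrow reading is the better one.

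**Inputs.**
- Treatment lasts 28 days (Protocol 3.2).
- All-cause collection ends at last dose + 30 days (Protocol 7.3).
- Follow-up is 24 weeks, 24 × 7 = 168 days; Week 12 is Day 84 and Week 24 is Day 168 (Protocol 6.5.3).
- Week 20 is 20 × 7 = Day 140 (nominal-day rule, SAP 3.8.3).
- The visit window is ±5 days (Protocol 6.5.2, 6.5.3).

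**Under 7.3.** Restricted days = 168 − (last dose day + 30).

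| Last dose of both drugs | All-cause collection ends | Restricted days | Share of 168 |
|---|---|---|---|
| Day 28 | Day 58 | 110 | 65% |
| Day 14 | Day 44 | 124 | 74% |
| Day 7 | Day 37 | 131 | 78% |

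**Under the visit lists, non-serious unrelated events.** The last visits that ask for all AEs are Week 8 and the 30-day follow-up visit (Day 58 for a completer), so 168 − 58 = 110 days (65%) again.

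**Under the visit lists, serious events.**
- All SAEs are asked for up to Week 12: 168 − 84 = 84 days restricted, 84/168 = 50%. The ±5 days give 79 to 89 days (47% to 53%).
- If the site follows the all-SAE bullet at Week 24 rather than the narrow bullet beside it, that bullet reaches back only to the previous visit, Week 20. Day 84 to Day 140 stays restricted: 140 − 84 = 56 days, 56/168 = 33%.
- The count is 0 only under the synopsis, or under Appendix 2 with SAP 1.2.

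**mITT tables only.** Protocol 6.7 withdraws subjects whose biopsy is not consistent with AH after the 30-day visit. SAP 3.1.2 keeps them in the mITT set, on which the secondary set of end-of-study tables is based. Their number is not given. They are outside the FAS, the primary efficacy set (SAP 3.1.3).

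**Footnote t.** It has anyone stopping before Week 4, for any reason, seen at 30 days and then withdrawn. Protocol 6.7 keeps confirmed-AH subjects in all follow-up visits, and 3.2 does so for those stopping both drugs before Week 2.

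**The case against.** The best defence is that 7.3 is a general safety rule and the endpoint passages are a specific rule on top of it. SAP 1.2 says this outright, and the SAP states that it was written from Amendment 3 and the eCRF. The AE form has a dedicated infection field. HRS and infection are assessed at every late visit, and 6.9.8 asks for HRS dates and therapies with no time limit. Data are routinely queried for completeness (Protocol 9.1.6). Entry also follows eCRF completion guidelines that are not among the documents. If those match SAP 1.2, nothing may have been lost.

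This stands as a reason not to assert a loss. It does not remove the conflict: 7.3 is the section that tells sites what to report, it contains no exception for endpoint events, and 6.5.2 repeats it visit by visit. SAP 6.2.7 tabulates medications for infection and HRS, but does not plan to compare them with the AE records.

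Four further inferences are tempting, and the documents do not carry them:
- **The arms are biased.** The cutoff moves with each subject's last dose, so unequal stopping could matter, but nothing shows that it did.
- **The Week 24 all-SAE bullet closes the gap for serious events.** It covers only the time since Week 20.
- **20 of 120 subjects (17%) were lost to late follow-up in the mITT set.** That is a planning allowance for AH not confirmed on biopsy. It includes inadequate biopsies, and those subjects may remain in the study (Protocol 3.2, 6.8).
- **Competing-risk analysis is needed.** The planned infection and HRS summaries are descriptive counts, and cumulative incidence would be a preference.

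**Conclusion.** The contradiction is established from the text; the undercount is possible but not shown. A site that followed 7.3 alone could leave out late infections and HRS unrelated to drug or procedure on 110 of 168 days for a 28-day completer, and on 131 for a subject whose last dose was on Day 7. For serious events the visit lists leave 84 or 56 days restricted, according to which Week 24 bullet is used; other passages leave none. These figures assume nominal visit days and measure exposure to the narrow rule. They cannot be turned into missing events, because the documents do not give the timing of infections or HRS.

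The primary analysis of treatment-emergent AEs ends at last dose plus 30 days and is not affected. The mITT point concerns secondary tables only, with an unknown number of subjects. Footnote t is a drafting conflict with 6.7 and 3.2. The matter should be fixed before the final analysis, but it does not put the trial's main conclusion at risk.

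**What to change.** 1. Reconcile 7.3, 6.5.2, 6.5.3 and the synopsis with Appendix 2 footnote e and SAP 1.2, so that infections and HRS are recorded to Week 24 regardless of cause. Reconcile footnote t with 6.7.
2. While queries are still being resolved (SAP 2.4), query every post-treatment medication with an indication of infection or HRS, and every listed positive culture, that has no matching AE. Screen out prophylaxis. This finds only treated or cultured events.
3. If capture proves incomplete, also report both endpoints over the period in which all-cause collection was required, each subject's last dose plus 30 days, and label the end-of-study counts as incomplete. A fixed Week 8 cutoff would not do: since 26 + 30 = 56, a subject who stops both drugs before Day 26 leaves the 7.3 window before Day 56.
4. State in the CSR that this reporting was added after unblinding at the primary analysis (SAP 2.3).
5. Footnote the mITT tables with the number of subjects withdrawn after the 30-day visit.

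The cost is a few queries, one or two extra tables and some wording; no new visits. Protocol rewording needs IRB/IEC approval (Protocol 9.2.1) and cannot by itself recover data already collected, so the query is the step that matters most now. Cumulative incidence with death and transplant as competing events is optional.
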